4.2 Number of Subjects

Approximately **1400** subjects will be enrolled in the study; all subjects are to receive erenumab, either 70 mg or 140 mg SC Q4W, determined at the investigator's discretion and may be adjusted once during the study at the week 12 visit.

Subjects in this clinical investigation shall be referred to as "subjects". For the sample size justification, see [Section 9.1](#).

4.2.1 Replacement of Subjects

Subjects who are withdrawn or removed from treatment or the study will not be replaced.

4.2.2 Number of Sites

Approximately 2 to 4 investigative sites in Europe will be included in the study. Sites that do not enroll subjects within 6 months of site initiation may be closed.

4.3 End of Study

4.3.1 End of Study Definition

End of Study: An individual subject is considered to have completed the study if he/she has completed the last scheduled procedure shown in the Schedule of Activities ([Table 1](#)). The end of study date is defined as the date when the last subject across all sites is assessed or receives an intervention for evaluation in the study (ie, last subject last visit), following any additional parts in the study (eg, long-term follow-up), as applicable.

4.3.2 Study Duration for Subjects

The study duration including screening/baseline period and 24-week open-label treatment period is approximately 28 to 33 weeks.

4.4 Justification for Investigational Product Dose

Erenumab 70 mg and 140 mg SC Q4W are approved in Europe and the United States for the prevention of migraine in adults. Regulatory approval was granted on the basis of established superiority against placebo for each dose in 4 independent randomized clinical studies (1 CM and 3 EM) (Sun et al, 2106; Goadsby et al, 2017; Tepper et al, 2017; Dodick et al, 2018).

4.5 Patient Input on Study Design

Patient input was not solicited in the study design.

5. Study Population

Investigators will be expected to maintain a screening log of all potential study candidates that includes limited information about the potential candidate (eg, date of screening).

Eligibility criteria will be evaluated during screening.

Before any study-specific activities/procedures, the appropriate written informed consent must be obtained (see Section 11.3).

Prospective approval of protocol deviations to recruitment and enrollment criteria, also known as protocol waivers or exemptions will not be provided.

5.1 Inclusion Criteria

Subjects are eligible to be included in the study only if all of the following criteria apply:

Before baseline period

- 101 Subject has provided informed consent prior to initiation of any study-specific activities/procedures.
- 102 Age \geq 18 years upon entry into screening
- 103 History of migraine (with or without aura) for \geq 12 months before screening according to the International Headache Society (IHS) Classification ICHD-3 (Headache Classification Committee of the International Headache Society, 2018) based on medical records and/or patient self-report
- 104 \geq 4 headache days that meet criteria as migraine days per month on average across the 3 months before screening

After baseline period

- 105 Must have demonstrated \geq 75% compliance in eDiary usage during baseline period

5.2 Exclusion Criteria

Subjects are excluded from the study if any of the following criteria apply:

Disease Related

- 201 > 50 years of age at migraine onset
- 202 History of cluster headache or hemiplegic migraine headache
- 203 Inability to differentiate between migraine from other headaches

Other Medical Conditions

- 204 The subject is at risk of self-harm or harm to others as evidenced by past suicidal behavior
- 205 History or evidence of any other clinically significant disorder, condition or disease (with the exception of those outlined above) that, in the opinion of the investigator or Amgen physician, if consulted, would pose a risk to subject safety or interfere with the study evaluation, procedures or completion

Prior/Concomitant Therapy

- 206 Previously received erenumab (Aimovig)
- 207 Received an anti-CGRP monoclonal antibody within 3 months prior to the start of the baseline period
- 215 Initiation, discontinuation, or change of dosing of migraine prophylactic medications within 2 months prior to the start of the baseline period, during the baseline period or planned during the study. Refer to Section [6.1.7](#) for additional information.

Prior/Concurrent Clinical Study Experience

- 208 Currently receiving treatment in another investigational device or drug study, or less than 30 days or 5 half-lives since ending treatment on another investigational device or drug study(ies). Other investigational procedures while participating in this study are excluded.

Other Exclusions

- 209 Female subjects of childbearing potential with a positive pregnancy test assessed at screening or day 1 by a urine pregnancy test.
- 210 Female subject is pregnant or breastfeeding or planning to become pregnant or breastfeed during treatment and for an additional 16 weeks after the last dose of investigational product.
- 211 Female subjects of childbearing potential unwilling to use 1 acceptable method of effective contraception during treatment and for an additional 16 weeks after the last dose of investigational product. Refer to Section [11.5](#) for additional contraceptive information.
- 212 Evidence of current pregnancy or breastfeeding per subject self-report or medical records
- 213 Subject has known sensitivity to any of the products or components to be administered during dosing.
- 214 Subject likely to not be available to complete all protocol-required study visits or procedures, and/or to comply with all required study procedures (eg, Clinical Outcome Assessments) to the best of the subject and investigator's knowledge.

5.3 Subject Enrollment

Before subjects begin participation in any study-specific activities/procedures, Amgen requires a copy of the site's written institutional review board/independent ethics committee (IRB/IEC) approval of the protocol, informed consent form (ICF), and all other subject information and/or recruitment material, if applicable (see Section [11.3](#)).

The subject must personally sign and date the IRB/IEC and Amgen approved informed consent before commencement of study-specific procedures.

A subject is considered enrolled when the investigator decides that the subject has met all eligibility criteria. This should occur on day 1, after completion of the baseline period. The investigator is to document this decision and date, in the subject's medical record and in/on the enrollment electronic case report form (eCRF).

Each subject who enters into the screening period for the study (defined as when the subject signs the ICF) receives a unique subject identification number before any study-related activities/procedures are performed. The subject identification number will be assigned sequentially following format provided by Amgen. This number will be used to identify the subject throughout the clinical study and must be used on all study documentation related to that subject.

The subject identification number must remain constant throughout the entire clinical study; it must not be changed after the initial assignment, including if a subject is rescreened.

5.4 Screen Failures

Screen failures are defined as subjects who consent to participate in the clinical study but are not subsequently enrolled in the study. A minimal set of screen failure information will be collected that includes demography, screen failure details, eligibility criteria, medical history, prior therapies, and any serious adverse events.

Individuals who do not meet the criteria for participation in this study (screen failure) may be rescreened once if in the opinion of the investigator, the reason for the initial screen failure has been resolved or is no longer applicable. Refer to Section [8.1.1](#).

6. Treatments

Study treatment is defined as any investigational product(s), non-investigational product(s), placebo, or medical device(s) intended to be administered to a study subject according to the study protocol.

Note that in several countries, investigational product and non-investigational product are referred to as investigational medicinal product and non-investigational medicinal product, respectively.

The Investigational Product Instruction Manual (IPIM), a document external to this protocol, contains detailed information regarding the storage, preparation, destruction, and administration of each treatment shown in [Table 3](#) below.

6.1 Treatment Procedures

6.1.1 Investigational Products

Table 3. Study Treatments

Study Treatment Name	Amgen Investigational Product:^a Erenumab
Dosage Formulation	Erenumab will be packaged in a SureClick® AI/Pen containing 1 mL of 70 mg/mL or 140 mg/mL of erenumab.
Unit Dose Strength(s)/ Dosage Level(s) and Dosage Frequency	Erenumab 70 mg or 140 mg will be administered Q4W. Dose is to be determined at the investigator's discretion and may be adjusted once during the study at the week 12 visit.
Route of Administration	SC injection
Accountability	The quantity, start date, and lot number of investigational product are to be recorded on each subject's eCRF.
Dosing Instructions	Site staff is to dispense erenumab AI/Pens to subjects at the day 1 visit (for treatment on day 1, week 4, and week 8) and week 12 visit (for treatment at weeks 12, 16, and 20). At the day 1 and week 12 visit erenumab will be administered to subjects by site staff or by subject self-administration as the last procedure of the visit. Administration will be performed by the subject or designee in a non-investigator site setting (eg, at home) at weeks 4, 8, 16, and 20. At week 4, subjects participating in the CGRP biomarker substudy are to be instructed to administer erenumab dose at non-investigative site (eg, home) after the visit.
Device	Refer to the IPIM for investigational product details. AI/Pen

AI = autoinjector; eCRF = electronic case report form; IPIM = Investigational Product Instruction Manual; Q4W = once every 4 weeks; SC = subcutaneous.

^aErenumab will be manufactured and packaged by Amgen and distributed using Amgen clinical study drug distribution procedures.

6.1.2 Non-investigational Products

Non-investigational products will not be used in this study.

6.1.3 Medical Devices

The following investigational medical device(s) provided by Amgen for use in this study is the erenumab SureClick® Autoinjector Pen (AI/Pen) ([Table 3](#)).

The erenumab SureClick® AI/Pen is a single-use disposable, handheld mechanical “spring-based” device for fixed dose SC injection of erenumab 1 mL deliverable volume.

Additional details are provided in the IPIM.

Other non-investigational medical devices may be used in the conduct of this study as part of standard care.

Non-investigational medical devices (eg, syringes, sterile needles), that are commercially available are not usually provided or reimbursed by Amgen (except, for example, if required by local regulation). The investigator will be responsible for obtaining supplies of these devices.

6.1.4 Other Protocol-required Therapies

Other-protocol-required therapies will not be used in this study.

6.1.5 Other Treatment Procedures

Other treatment procedures will not be conducted in this study.

6.1.6 Product Complaints

A product complaint is any written, electronic or oral communication that alleges deficiencies related to the identity, quality, durability, reliability, safety, effectiveness, or performance of a drug, **combination product**, or device after it is released for distribution to market or clinic by either **(1)** Amgen or **(2)** distributors **or** partners for whom Amgen manufactures the material.

This includes all components distributed with the drug, such as packaging drug containers, delivery systems, labeling, and inserts.

This includes any investigational/non-investigational product(s), device(s), or combination product(s) provisioned and/or repackaged/modified by Amgen, including the erenumab AI/Pen.

Any product complaint(s) associated with an investigational product(s), non-investigational products devices(s), or combination product(s) supplied by Amgen are to be reported according to the instructions provided in the IPIM.

6.1.7 Excluded Treatments, Medical Devices, and/or Procedures During Study Period

Concomitant treatment with migraine prophylactic medications are allowed under the following conditions:

- Drug regimen (ie, formulation, frequency of use, route, and dose) is stable for \geq 2 months (for oral migraine prophylactic medications) or \geq 2 cycles (for botulinum toxin) prior to the start of the baseline period
- Drug regimen is at a generally accepted dose, frequency, and route for its use in migraine
- Drug regimen is not anticipated to change during baseline period or throughout the study

Allowable medications include:

- Antiepileptics (eg, divalproex sodium, sodium valproate, topiramate, carbamazepine, levetiracetam)
- Angiotensin receptor blockers (eg, candesartan) or ACE inhibitors (eg, lisinopril)
- Beta blockers
- Calcium channel blockers (eg, verapamil, amlodipine, cinnarizine) or calcium antagonists (eg, flunarizine)
- Tricyclic antidepressants
- Other antidepressants (eg, serotonin-norepinephrine reuptake inhibitors, selective serotonin-reuptake inhibitors)
- Botulinum toxin (in the head and/or neck region)
- Other drugs used for migraine prevention (eg, clonidine, guanfacine, methysergide, cyproheptadine, pizotifen), except for anti-CGRP medications which are excluded.

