1.3 Schedule of Activities

Table 1. Schedule of Activities

	Screening ^a (up to 21 days before baseline)	Baseline ^a (28 [+7] days before day 1)	Open-label Treatment Period (24 weeks)							Notes
			Day 1 visit	Wk 4 (± 7 days)	Wk 8 (± 7 days)	Wk 12 (± 7 days)	Wk 16 (± 7 days)	Wk 20 (± 7 days)	Wk 24/EOS ^b (± 7 days)	
GENERAL AND SAFETY ASSESSMENTS										
Informed consent	X									
Inclusion and exclusion criteria	X	X	X							Compliance with eDiary usage will be assessed prior to enrollment on day 1
Demographics	X									
Medical history	X									
Neurological medical history	X									
Gastro-intestinal medical history	X									Includes gastro-intestinal procedures and surgeries medical history
Headache and migraine frequency medical history	X									
Prior migraine prophylactic medications review	X	X								Includes all prior migraine prophylactic medications that ended 2 months before screening with no limit back in time.

	Screening ^a (up to 21 days before baseline)	Baseline ^a (28 [+7] days before day 1)	Open-label Treatment Period (24 weeks)							Notes
			Day 1 visit	Wk 4 (± 7 days)	Wk 8 (± 7 days)	Wk 12 (± 7 days)	Wk 16 (± 7 days)	Wk 20 (± 7 days)	Wk 24/EOS ^b (± 7 days)	
Prior/concomitant therapies review	X	X	X			X			X	Includes all prior medications (other than prior migraine prophylactic medications) that were being taken/used within 120 days prior to screening through the signing of the informed consent and all concomitant medications including migraine prophylactic medications.
Most recent date of menses	X		X			X			X	Females of childbearing potential only

Page 1 of 2

Footnotes after last page of table

	Screening ^a (up to 21 days before baseline)	Baseline ^a (28 [+7] days before day 1)	Open-label Treatment Period (24 weeks)							Notes
			Day 1 visit	Wk 4 (± 7 days)	Wk 8 (± 7 days)	Wk 12 (± 7 days)	Wk 16 (± 7 days)	Wk 20 (± 7 days)	Wk 24/EOS ^b (± 7 days)	
SAFETY ASSESSMENTS										
Adverse events			Adverse events collected from day 1 to EOS							
Serious adverse events			Serious adverse events collected from screening to EOS							
Adverse device effects			Adverse device effects collected from day 1 to EOS							

	Screening ^a (up to 21 days before baseline)	Baseline ^a (28 [+7] days before day 1)	Open-label Treatment Period (24 weeks)							Notes
			Day 1 visit	Wk 4 (± 7 days)	Wk 8 (± 7 days)	Wk 12 (± 7 days)	Wk 16 (± 7 days)	Wk 20 (± 7 days)	Wk 24/EOS ^b (± 7 days)	
LABORATORY ASSESSMENTS										

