6.8 Prior and Concomitant Treatment

6.8.1 Prior Treatment

All prior prophylactic migraine therapies ever taken and ending prior to start of baseline will be collected, including reason for ending therapy.

For all other prior therapies that were being taken/used from 120 days before screening through the signing of the informed consent, therapy name, start date, and stop date will be collected.

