4.1 Planned Covariates

All models will be adjusted for age and sex. In addition, all model-adjusted analyses of efficacy endpoints assessing change from baseline will include the corresponding baseline value for the endpoint being analyzed. All models that compare baseline measurements only will be adjusted for country. However, country will not be included as a covariate in any deCODE performed analyses since all deCODE analyses will be performed separately by country (Denmark/Iceland) and subsequently combined in a meta-analysis. Due to the high correlation between baseline dose and country, models assessing change from baseline will instead be adjusted for baseline dose (70mg/140mg) and dose switch only.

Principal components of genotype data will be adjusted for population stratification in mPRS related analysis. Calculation of principal components data will be described in the analysis plan developed by deCODE.

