5.7 Disease Characteristics

Treatment Failure of Prior Migraine Preventive Medications

Treatment failure of prior migraine preventive medications is determined by “Reason for Stopping” as “Lack of efficacy” or “Adverse reaction” on the Prior Migraine Prophylactic Medication eCRF.

Menstrual-related migraine

If a female patient responds yes to the question “Does the subject report migraine attacks that occurred on day 1 +/- 2 of menstruation (ie Days -2 to +3, day 1 = start of menstruation) in at least two out of the last three menstrual cycles prior to screening?” in the Headache and Migraine Frequency History eCRF then the patient will be considered in the subgroup menstrual-related migraine.

6. Analysis Sets

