	
regression model including baseline CGRP, age, sex, dose switch (yes/no), baseline dose (full sample analysis only), and baseline MMD value as covariate using observed data. Dose switch was excluded for 140 mg treatment group.
 
3. Spearman correlation between baseline non-transformed CGRP and Change from baseline in MMD over months 4, 5, and 6.
 
4. A scatterplot with loess will developed for CGRP level with change from baseline in monthly MMD over months 4, 5, and 6.

Achievement of at least a 50% reduction from baseline in mean MMD over months 4, 5, and 6 in relation to baseline CGRP level	
1. Summary statistics based on observed data.2. Odds ratio estimate for baseline CGRP, associated 95% CI, and nominal p-value from a logistic regression model with baseline CGRP level as covariate along with baseline MMD, dose switch (yes/no), baseline dose (full sample analysis only), age and sex. Dose switch was excluded for 140 mg treatment group.3. Predicted probabilities of achieving at least a 50% reduction in MMD
Achievement of at least a 75% reduction from baseline in mean MMD over months 4, 5, and 6, in relation to baseline CGRP level	Same as above.
Change from baseline in monthly AMSMD over months 4, 5, and 6, in relation to baseline CGRP level	
1. Estimated slope for baseline CGRP, associated 95% CI and nominal p-value from a linear regression model including baseline CGRP, age, sex, dose switch (yes/no), baseline dose (full sample analysis only), and baseline AMSMD value as covariate using observed data. Dose switch was excluded for 140 mg treatment group.2. Spearman correlation analysis will be applied between baseline CGRP and change from baseline in monthly AMSMD over months 4, 5, and 6.3. A scatterplot with loess will developed for CGRP level with change from baseline in monthly AMSMD over months 4, 5, and 6.
Baseline MMD in relation to baseline CGRP level	
1. Summary statistics using observed data.2. Estimated slope for CGRP, associated 95% CI and nominal p-value from a linear regression model including age, sex, country (full sample analysis only), and baseline CGRP as covariate using observed data.3. Spearman correlation between baseline CGRP and baseline MMD.

Endpoint	Primary Summary and Analysis Method

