9.6.3 Exposure to Concomitant Medication

Number and proportion of subjects receiving **acute headache medication or triptan** will be summarized **for baseline and post-baseline.**

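### Ongoing migraine preventives are allowed and recorded but enter no planned model, subgroup or summary, so the CGRP-response results could be confounded and the no-prior-failure group is mixed

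*Protocol*

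**What the plan says.** **Permitted and recorded.** Protocol 6.1.7 states: "Concomitant treatment with migraine prophylactic medications are allowed under the following conditions". The regimen must be stable before baseline, generally accepted for migraine, and not expected to change. The allowed list covers antiepileptics, beta blockers, calcium channel blockers, antidepressants, botulinum toxin and others; anti-CGRP drugs are excluded. The Schedule of Activities (Protocol 1.3, Table 1) collects "all concomitant medications including migraine prophylactic medications".

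**Models.** SAP 4.1 begins: "All models will be adjusted for age and sex". It adds the baseline value of the endpoint and, for baseline-only comparisons, country. Otherwise "models assessing change from baseline will instead be adjusted for baseline dose (70mg/140mg) and dose switch only". In SAP 9.5, Table 8, the logistic model for 50% response is fitted "with baseline CGRP level as covariate along with baseline MMD, dose switch (yes/no), baseline dose (full sample analysis only), age and sex". Appendix B lists age, sex, dose switch and baseline value, plus principal components for Denmark.

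**Subgroups and summaries.** The only subgroup about preventives is prior treatment failure (SAP 4.2, Appendix B). SAP 5.7 reads: "Treatment failure of prior migraine preventive medications is determined by" the recorded reason for stopping, either lack of efficacy or an adverse reaction. The baseline list in SAP 9.4 has prior preventive use only, and Protocol 6.8.1 describes prior therapy as: "All prior prophylactic migraine therapies ever taken and ending prior to start of baseline will be collected, including reason for ending therapy". SAP 9.6.3 starts "Number and proportion of subjects receiving" and goes on to acute headache medication or triptan, not preventives.

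**The concern.** Where a subject takes a background preventive, baseline migraine days, baseline CGRP and the months 4 to 6 response are all measured on top of it. No randomised comparator balances that factor. Users may have disease that is harder to treat, and their CGRP level may differ. If both hold, a model of response on CGRP that omits ongoing use attributes part of the users' difference in response to CGRP.

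The plan adjusts for dose switch, which happens after treatment starts, but not for this pre-treatment factor.

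The second issue is the prior-failure subgroup of the primary endpoint. A drug still being taken has no reason for stopping, so it cannot count as a failure. The no-failure category therefore holds at least two kinds of subject: those who never took a preventive, and those taking one now with no earlier drug stopped for lack of efficacy or adverse reaction. A reader of the subgroup table would not see how many of each it contains.

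**Working it through.** **Step 1: text trace.** The plan disputes no figure here, so the main check is whether ongoing preventive use appears anywhere in the analysis.

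| Place | Preventive-related content |
|---|---|
| SAP 4.1, Table 8 | none |
| SAP Appendix B covariates | none |
| SAP 4.2 and Appendix B subgroups | prior failure only |
| SAP 9.4 baseline list | prior use only |
| SAP 9.6.3; Protocol 9.3.2.3.3 | acute medication (SAP: or triptan) only |
| SAP 8.4 bias factors | not listed |

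Ongoing use is in no model, no subgroup and no planned summary.

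**Step 2: size of possible confounding in the 50% response model.** From the documents: 1400 × (1 − 0.10) = 1260 subjects, and about 50% response (Protocol 9.1). *Assumed, because the documents give nothing:* share of users p = 0.3 to 0.5; CGRP lower in users by d = 0 to 0.5 SD; odds of response lower in users by a factor R = 1.5 to 2.0; no true CGRP effect.

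First-order bias in the log odds ratio per SD of CGRP (SD within user group):

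b = ln(R) × p(1 − p)d / [1 + p(1 − p)d²]

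Standard error ≈ 2/√1260 = 0.0563. Rejection rate ≈ Φ(b/SE − 1.96) + Φ(−b/SE − 1.96).

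| p | d | R | b | OR per SD | b/SE | Rejection at nominal 5% |
|---|---|---|---|---|---|---|
| any | 0 | any | 0 | 1.00 | 0 | 5% |
| 0.3 | 0.2 | 1.5 | 0.405 × 0.042/1.0084 = 0.017 | 1.02 | 0.30 | 6% |
| 0.5 | 0.2 | 2.0 | 0.693 × 0.05/1.01 = 0.034 | 1.03 | 0.61 | 9% |
| 0.5 | 0.5 | 2.0 | 0.693 × 0.125/1.0625 = 0.0815 | 1.08 | 1.45 | 30% |

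The last row takes the extreme value of all three inputs.

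**Step 3: sensitivity to the assumptions.** A separate simulation used 20% to 40% users, CGRP *higher* in users by 0 to 0.5 SD, and a response odds ratio of 0.8 to 0.4 for users against non-users. The spurious odds ratio then ran from 1.00 down to 0.90, with rejection from 5% to about 46%. The 46% needs 40% users, a 0.5 SD shift and an odds ratio of 0.4 together. At a 0.2 SD shift rejection was 5% to 11%. The sign follows the assumed sign of the CGRP shift, so the documents do not fix the direction.

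Both calculations leave out baseline MMD, age, sex and dose, which the planned model contains.

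**Step 4: mixing in the no-failure group (illustration, all rates assumed).** Let a share q of the group be on a current preventive and respond at rate r, with the rest responding at 60%. The pooled rate is (1 − q) × 60% + q × r. With q = 10%, r = 50% it is 59%; with q = 50%, r = 30% it is 45%.

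**The case against.** **Confounding is assumed.** It needs a link to CGRP and a link to response, and the documents show neither. This stands: with no CGRP shift there is no bias at all. A reader might infer that the CGRP results *are* biased, and the documents do not support that.

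**The analyses are descriptive.** SAP 2.2 disclaims formal testing and Table 8 p-values are nominal. If CGRP is read purely as a predictor in the enrolled population, the estimate without this covariate is a legitimate target. This also stands, and it argues for showing both estimates rather than replacing one.

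**The design helps.** Exclusion 215 and Protocol 6.1.7 require stable regimens, and baseline value is a covariate. This reduces the problem without removing it.

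**The genetic models.** A reader might infer that the primary SNP analysis needs the same adjustment. Genotype precedes drug use, and Protocol 2.1 reports an association of mPRS with prophylactic medication use. Ongoing use may therefore lie downstream of genotype, and conditioning on it could remove real association or create a spurious one. This objection is correct.

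**Two further readings go too far.** The number of subjects on add-on therapy is not unknowable: the data are collected and only the table is unplanned. Nor can those on a current preventive be called uncontrolled on it. The entry rule of at least 4 migraine days covers the 3 months before screening, stability of oral drugs is required only for 2 months before baseline, and no minimum is set for the baseline period.

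**The subgroup is labelled prior failure and defined accordingly.** True, but its no-failure side still pools different subjects without saying so.

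**Conclusion.** The gap in the text is certain: a permitted, recorded background treatment appears in no planned output, and the no-failure category mixes currently treated with never-treated subjects. That category may also include subjects who stopped a drug for other reasons.

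The confounding of the Table 8 CGRP-response slopes and odds ratios is conditional. For the 50% response model it runs from nothing to an odds ratio per SD of about 1.08 and a nominal error near 30%, the latter only at the extreme of every input in that range. A still stronger assumed association with response pushes it further. All of these sizes rest on assumptions about the share of users, the CGRP shift and the effect on response. The slopes for change in migraine days and medication days were not sized.

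This is a worthwhile low-cost improvement to exploratory analyses and to one subgroup display. It is not a defect in the primary SNP analysis.

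**What to change.** 1. Derive a flag, migraine preventive ongoing at day 1 (yes/no), from the concomitant-medication eCRF.
2. Report it in the SAP 9.4 baseline table.
3. Run the Table 8 models of response or change on baseline CGRP with and without the flag as a covariate, and show both.
4. Report the no-prior-failure group split by the flag.
5. Leave it out of the main SNP and mPRS models. At most, use it there as a with/without sensitivity run, as Appendix B already does for dose switch and baseline value.

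A yes/no flag will not capture differences between drug classes, so agreement of the two runs would be reassuring but not proof.

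The cost is SAP wording, one derived variable, one degree of freedom per model and one more set of runs. Some allowed classes, such as beta blockers and antidepressants, have non-migraine uses. The documents do not say whether the eCRF records indication, so medical review may be needed to assign it. No visit, treatment rule or sample size changes.
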